5.6 Concomitant and Excluded Therapy

Concomitant medications are any prescription medications or over-the-counter preparations used by the subject between 7 days prior to enrollment (30 days for anticoagulants) and 30 days following IUS discontinuation. All concomitant medications, including excluded therapies, must be documented in the Concomitant Medication CRF. Subjects who begin to chronically use excluded therapies may require discontinuation from the study. The Medical Monitor should be contacted to discuss possible discontinuation of these subjects.

The following concomitant therapies are excluded while on study treatment:

- Hormonal contraceptives with the following exceptions:
 - An oral, transdermal, vaginal or combined monthly injectable hormonal contraceptive may be used in the first month only as outlined in Section 6.3;
 - Emergency contraception should be recommended in any situation when the subject feels the IUS expelled and she subsequently had intercourse. Subjects will not be discontinued from the study because of emergency contraceptive use.
- A previously inserted contraceptive implant, IUD or IUS unless the implant, IUD or IUS is removed prior to study IUS insertion (may be removed immediately before study IUS insertion).
- Any other contraceptive method that could obscure the efficacy parameters of this investigational contraceptive should not be used during study participation. However, if the subject feels the need to protect herself against sexually transmitted infections, she should be advised to use a male condom. If the use of a male condom becomes a regular part of the subject's contraception, the site Principal Investigator should check with the Medical Monitor

about possibly discontinuing the subject from study participation. All condom usage will be documented on the daily subject diaries.

- Any non-contraceptive estrogen, progesterone, testosterone, or gonadotropin (e.g. hCG)
- Misoprostol on day before or day of IUS insertion or removal
- Any cervical dilating instrument used during IUS insertion other than Pratt dilators, a lacrimal duct probe or an os finder
- Any investigational treatment or medication other than the LNG20.

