6.3 Screening/Enrollment Visit

Screening is considered to start with the signing of the Informed Consent Form by the subject. Although the Screening and Enrollment Visits may occur during one visit, the Screening procedures may be performed over multiple days. The Enrollment Visit is considered to be on the date the subject is assigned through the IVRS. Screening test results are not required to be available prior to the Enrollment Visit.

Scheduling of the Enrollment Visit must take the following schemes into account:

- When switching from an oral, transdermal or vaginal hormonal contraceptive, the subject should continue that method after the study IUS insertion until the end of the current cycle. If using the contraceptive continuously (without a hormone free interval), then discontinue 7 days after IUS insertion. When possible, the Enrollment Visit should be scheduled during the hormone-free time of the cycle (i.e., “placebo week,” “patch-free week,” or “ring-free week”)
- When switching from an injectable monthly combined hormonal injection, the study IUS insertion may occur anytime within 28 days of the last injection
- When switching from non-hormonal contraception (except copper IUD), the study IUS insertion **must** be performed within the first 7 days of the menstrual cycle

- When switching from a contraceptive implant, another hormonal IUS, or a copper IUD, the study IUS insertion may occur anytime in the menstrual cycle but should occur on the same day as removal of the implant, non-study IUS, or IUD
- Women who need a screening Pap test (see section 6.11) should be scheduled for screening on a day they are expected to have minimal or no bleeding
- All enrollment procedures must be completed within 30 days of screening. If greater than thirty days, Medical Monitor approval must be obtained before rescreening or enrollment

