6.5 Contacts Between Study Visits

Telephone or e-mail contacts for safety evaluation will occur at the end of 9, 15, 21, 27, 33, 39, 45, 51, 57, 63, 69, 75, 81, 87, 93, 99, 105, 111 and 117 months of use (LNG20 36-45 year old enrollment group only through Month 93 and Mirena subjects only through Month 57). The contacts should occur within 14 days before or after the expected contact date.

- Review of adverse events or changes in medical history
- Review of concomitant medications
- Review contraception method history since last scheduled study contact. The IUS would be considered to be her primary method of contraception if no regular use of other contraception is indicated on the diaries.
- Complete Bleeding/Cramping Form
 - All subjects: Months 27, 33, 39, 45, 51 and 57
 - All LNG20 subjects: also Months 63, 69, 75, 81, 87, 93
 - LNG20 16-35 year old enrollment group: also Months 99, 105, 111 and 117
- Inquire about change in sexual partner. If a contact elicits that there has been a change in sexual partner since the last time the subject had STD testing, she should be asked to come to the office for an Unscheduled Visit for Chlamydia and gonorrhea testing. In addition, HIV and any other appropriate STD testing should be performed as per CDC recommendations.
- Interview subject regarding future plans for relocation or discontinuation
- LNG20 subjects who are beyond the Month 90 study visit at the time that an investigative site obtains Institutional Review Board approval of Protocol Version 9.0 will be informed about the amendment changes at the Month 93 telephone contact or, if the Month 93 telephone contact has already occurred, at an additional telephone contact.

- Telephone contact prior to any early IUS discontinuation:
 - Discuss contraception options in preparation for the upcoming Discontinuation Visit such that the subject can immediately initiate another method (the site should attempt to have her desired method available) or be abstinent to:
 - Avoid conception within 7 days after IUS discontinuation
 - Enable the subject to avoid undesired pregnancy
 - Request the subject not have intercourse for at least 24 hours before the Discontinuation Visit; the visit may need to be rescheduled if the subject has intercourse within 24 hours of IUS removal
- Confirmation of next scheduled appointment

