9.7 Primary Outcome

The Pearl Index at two years for women in the MITT population who received LNG20 is the primary efficacy endpoint. Pearl indices and life table pregnancy analyses will be presented by treatment group using the MITT population

The Pearl Index and 95% confidence interval will be used to establish efficacy for 2 years of use. Pregnancies in the MITT population to be included in the primary analysis are those that occurred while a study IUS was in place (determined by ultrasound and medical assessments) or

following unrecognized IUS expulsion. For clarification, if a pregnancy occurs in a woman with a known date of IUS expulsion, and that pregnancy occurred while not on study treatment or up to and including 7 days after IUS discontinuation, that pregnancy will not be counted in the primary analysis. Cycles (defined as 28-day intervals) where backup methods of contraception were used will be excluded from the primary analysis of the Pearl Index unless the subject became pregnant in that cycle. To establish the efficacy of LNG20 for 2 years of use, acceptable precision of the Pearl Index must be reached during year 1 and, separately, during year 2, where acceptable precision is defined as the upper bound of the 95% confidence interval being no more than 1 unit above the point estimate of the Pearl Index. This hierarchical approach will not require adjustment to the acceptable precision required for the confidence interval of the Pearl Index.

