- If, during on-study contact with the subject (e.g., Month 9 Contact, Month 15 Contact, Month 21 Contact), she reports that the IUS is no longer in place, the date of contact minus 1 day or last date at which a pregnancy test was performed (at study site or outside laboratory with copy of report), whichever is later, will be used as the last date associated with IUS use.
- Subjects who become pregnant with the IUS still in place will have their estimated date of conception used as the last IUS use date.
- In the cases of subjects who are lost to follow-up or withdraw consent prior to IUS removal and neither a last contact date nor a last pregnancy test date is available, the IUS insertion date + 1 day will be used as the last date associated with IUS use.

Similarly, for subjects who had a successful IUS insertion but who have not yet had any post-insertion data (e.g., diaries or post-insertion pregnancy test results) retrieved at the site which could be used to directly calculate duration of use, the IUS insertion date +1 day will be used as the last date of IUS use for the purpose of analysis. For the summary of duration of product use, all subjects with ≥ 1 days of product use, as defined in this section, will be included in the calculations. For the evaluation of adverse events, subjects with less than one calculated complete 28-day cycle of use (at least 23 days) will be excluded unless such subjects reported an adverse event at any time during the first 28 days following IUS insertion (see Section 11.2: Adverse Events for more detail).

5.5 28-Day Cycles of Use Calculation for Efficacy Evaluation

In addition to the calculation of 28-day cycles based on last date of IUS use as described in Section 5.4, the efficacy evaluation requires the exclusion of cycles from the Pearl Index denominator where the use of other birth control methods was reported. Since this information is obtained exclusively from subject daily diaries, 28-day cycles of use need to be calculated from the diary data so as to be able to determine when the use of other birth control methods occurred.

Using the same algorithm described in Section 5.4, each recorded diary date between the IUS insertion date and the last calculated date of product use, inclusively, is compared to the IUS insertion date in order to calculate cycle number and day. Duration of use expressed as the number of 28-day cycles is then calculated as the maximum duration

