9.2 Primary Efficacy Variable

The primary efficacy variable is the Pearl Index, an estimation of the number of unintended pregnancies per 100 women-years of exposure. The Pearl Index is calculated as the number of "on treatment" pregnancies in the study divided by the total number of complete 28-day cycles of use (as defined in Section 5.5) in the study across all participating subjects, that result multiplied by 1300 (13 cycles x 100 years). In the case of subjects who are still on study at the time of a Pearl Index calculation, the last known date of product use (defined in Section 5.4) will be used in place of the IUS discontinuation date. A "last cycle" computed using this algorithm will be considered complete if it is at least 23 days in length. In addition, subjects who become pregnant will have that last cycle counted as completed for the Pearl Index calculation, regardless of length.

For the primary Pearl Index outcome using exposure information through Year 5, the MITT population will be used as the basis of exposure and all 28-day cycles where use of another birth control method was reported in the daily diary will be excluded from the total cycle count denominator. Diary days when no information regarding the use other birth control methods is reported will be considered days when no other birth control method use took place. The Pearl Index will be calculated using both the cumulative data

through Year 10 and as individual, non-cumulative year-by-year estimates (see Section 10.1).

For the definitive assessment of contraceptive efficacy, the Pearl Index and its 95% confidence interval will be considered the primary result for inferences.

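### The primary Pearl Index drops other-contraception cycles on diary evidence alone, so hormonal or emergency use held on the Concomitant Medication CRF but missing from the diary stays in the denominator

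*SAP*

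**What the plan says.** Protocol 9.7 states the rule by use and names no data source: cycles "where backup methods of contraception were used will be excluded from the primary analysis of the Pearl Index". A cycle in which conception occurred is kept. SAP 5.5 repeats the aim ("the efficacy evaluation requires the exclusion of cycles from the Pearl Index denominator where the use of other birth control methods was reported") and then restricts the source: "Since this information is obtained exclusively from subject daily diaries". SAP 9.2 does the same for the primary result; cycles where "use of another birth control method was reported in the daily diary will be excluded from the total cycle count denominator". Under SAP 1, the SAP prevails over the protocol on statistical analysis.

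Blanks count as no use. SAP 9.2 sets this convention: "Diary days when no information regarding the use other birth control methods is reported will be considered days when no other birth control method use" occurred. SAP 5.3.2 agrees, and SAP 5.3.1 treats a page that was never returned like blank days within a returned one.

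Protocol 5.6 gives a second record: "All concomitant medications, including excluded therapies, must be documented in the Concomitant Medication CRF". Hormonal contraceptives head its list of excluded therapies. Emergency contraception and first-month hormonal overlap are exceptions to that list, but both are still medications. SAP 5.3.4 shows that this CRF carries start and stop dates.

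On overlap at entry, Protocol 6.3 says: "When switching from an injectable monthly combined hormonal injection, the study IUS insertion may occur anytime within 28 days of the last injection". It also has users of oral, transdermal or vaginal methods continue them for a time after insertion.

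**The concern.** The exclusion exists so that the index reflects women relying on the IUS alone. A cycle also covered by another hormonal method carries little pregnancy risk. Counting it adds to the denominator and, as a rule, nothing to the numerator. The trial could hold dated evidence of that cover and not use it.

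The effect would fall on the result that SAP 9.2 names as primary for inference, in every year, and on the cycle-excluded life tables in SAP 9.3, which rest on the same adjustment. No planned analysis bounds it from above. The secondary index with no cycle exclusions puts more cycles back and moves the estimate further down.

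**Working it through.** **1. Which cycles can be missed**

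| Situation | Outcome under SAP 5.5 and 9.2 |
|---|---|
| Use in both diary and CRF | Excluded, correctly |
| Use on CRF, diary days blank | Counted |
| Use on CRF, diary page missing between returned pages | Counted |
| Diary stops early | Later cycles dropped (SAP 5.5 takes the smaller count), so no error |
| Monthly injection before insertion, still active in cycle 1 | May be counted; diaries are first dispensed at enrollment (Protocol 6.3.2) |
| Condoms | Diary is the stated source (Protocol 5.6); the CRF adds nothing |

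SAP 5.3.1 says missing diary records do not affect the cycle calculation. That is true of numbering cycles from the insertion date. It is not true of deciding which cycles to exclude.

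**2. Effect on the index**

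Let P be pregnancies, C counted cycles, and f the share of C with another method not shown in the diary.

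- Reported index = 1300 × P / C (SAP 9.2).
- Corrected index = 1300 × P / [C × (1 − f)] = reported / (1 − f). P does not change, because a pregnancy in a backup cycle still counts.

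The documents give no value for f, so there is no figure to reproduce and the range is assumed. Starting from 0.280, the planning ceiling in SAP 4:

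| f | Corrected index |
|---|---|
| 1% | 0.280 / 0.99 = 0.283 |
| 2.5% | 0.280 / 0.975 = 0.287 |
| 5% | 0.280 / 0.95 = 0.295 |
| 7.7% (one cycle in 13) | 0.280 / 0.923 = 0.303 |
| 10% | 0.280 / 0.90 = 0.311 |

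**3. Exposure from the plan's own inputs**

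Inputs (SAP 4): 1,600 women; discontinuation 20%, 19%, 17%, then 16% a year; 0.6 months lost per subject in year 1 and 0.3 in later years. I average the numbers at the start and end of each year and convert 12 months to 13 cycles.

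- Year 1: mean of 1,600 and 1,280 = 1,440; × 11.4 = 16,416 woman-months = 1,368 woman-years = 17,784 cycles.
- Year 2: mean of 1,280 and 1,036.8 = 1,158.4; × 11.7 = 13,553 woman-months = 1,129 woman-years = 14,683 cycles.

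Together this is about 29,970 woman-months, some three times the plan's floor of 10,000.

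Ceiling for first-month overlap: if every woman's first cycle were covered and unlogged, f = 1,600 / 17,784 = 9.0%, and 0.280 becomes 0.308 in year 1.

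**4. Precision criterion (upper limit minus estimate no more than 1)**

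The SAP text does not name the interval method; I use exact Poisson limits. At an index of 0.280 the expected pregnancies are 0.280 × 13.68 = 3.8 in year 1 and 0.280 × 11.29 = 3.2 in year 2.

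| Year, pregnancies | f = 0: index, upper, distance | f = 5%: index, upper, distance |
|---|---|---|
| Year 1, 3 | 0.219, 0.641, 0.42 | 0.231, 0.675, 0.44 |
| Year 2, 3 | 0.266, 0.776, 0.51 | 0.280, 0.817, 0.54 |

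The distance also scales by 1 / (1 − f), so it reaches 1 when f = 1 − (distance at f = 0). With 4 pregnancies that is 1 − 0.456 = 54.4% in year 1 and 1 − 0.553 = 44.7% in year 2. With fewer pregnancies, f would have to be larger still.

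Later years have less room. On the same inputs year 5 has 8,429 cycles (648 woman-years). With 2 pregnancies, close to the 1.8 expected at 0.280, the distance goes from 0.806 to 0.848 at f = 5%. Only at 4 pregnancies does f = 5% cross the line (0.963 to 1.013).

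**The case against.** The strongest reply is that the diary is meant to capture all other contraception, daily and for the whole of treatment. Sites collect it at each visit and check that other contraceptive use is entered correctly (Protocol 6.4), and a forgotten diary is completed by recall on a copy (SAP 5.3.1). This stands. A reader might infer that everything on the Concomitant Medication CRF stays in the denominator; only use absent from the diary does.

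A reader might also take the contact review in Protocol 6.5 ("Review contraception method history since last scheduled study contact") as a third, independent source. Its next sentence judges primary method by what the diaries show, and Protocol 6.4 and 6.6 likewise review diary entries. No separate dated field is described.

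The routes are narrow. Permitted hormonal overlap is confined to the first month. Emergency contraception is recommended when the woman feels the IUS has been expelled, and a confirmed expulsion ends treatment. Prolonged use of other contraception is referred to the Medical Monitor (Protocol 7.18.1). The SAP also has features that raise the index: a cycle with any reported use is dropped whole, the smaller cycle count is used, and a last cycle under 23 days is not counted. The direction claimed here is therefore that of this one component, not of the net estimate.

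Protocol 9.7 names no source, so the SAP narrows the rule and does not flatly contradict it. What remains is that the stated reason for using the diary alone is incorrect, and that neither document measures disagreement between the diary and the CRF.

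**Conclusion.** The point holds in a limited form. The diary-only rule rests on an incorrect premise. It can keep cycles with documented hormonal or emergency contraception in the primary denominator, and each such cycle lowers the index. The relative understatement equals f, which the documents do not give. I expect it to be small, since the diary is continuous and checked: 0.280 would be 0.283 to 0.311 for f of 1% to 10%. These figures assume that pregnancies are counted as planned. The exposure projection also assumes the plan's own discontinuation rates.

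A reader might infer that the two-year efficacy conclusion is in doubt. The documents do not support that: about 45% or more of a year's cycles would have to be affected, with up to 4 pregnancies, before the precision criterion failed in year 1 or 2. The matter is the accuracy of the primary estimate and the use of data already held. It should be corrected. The mention of Year 5 in the exclusion sentence of SAP 9.2 is a separate point.

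**What to change.** In SAP 5.5 and 9.2:

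1. Delete the word *exclusively* and its reasoning.
2. Exclude a 28-day cycle, unless conception occurred in it, if another method appears in the diary, or if a hormonal or emergency contraceptive on the Concomitant Medication CRF has dates overlapping that cycle.
3. State a separate date rule for this purpose. SAP 5.3.4 sets a missing stop date to the last date of product use, so one incomplete record could remove all later cycles. For example, exclude only cycles with documented overlap and show the wider imputation as a sensitivity analysis.
4. Identify combined monthly injections given within 28 days before insertion from the screening contraception history (Protocol 6.3.1), and exclude cycle 1 for those women. The medication history reaches back only 7 days before enrollment, so an injection 8 to 28 days earlier need not be on the CRF.
5. Report how many cycles were found outside the diary, and show the diary-only index alongside. Apply the same exclusions to the cycle-adjusted life tables.
6. Do not list visit or contact review as a source unless a dated field exists.

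Cost: SAP wording, a coded list of contraceptive medications, a date rule, and a merge with the CRF and screening history. No new data collection is needed if the screening history holds injection dates; that should be checked. The price is slightly fewer cycles and a slightly higher index with a slightly wider interval.

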5.6 Multiple Comparison/Multiplicity

Since no formal statistical tests are planned for this study, there are no provisions for multiple comparisons or multiplicity adjustment of study endpoints. The Pearl Index point estimate calculations for each of Years 1 through 10 will include 95% confidence intervals that assume an unadjusted two-sided $\alpha=0.05$. This is consistent with the manner in which the Pearl Index is derived in contraceptive efficacy studies. That is, the 95% confidence interval calculation is used as a tool in determining whether the extent of exposure in a given study is adequate to support the precision of the reported Pearl Index point estimate. Note that the Pearl Index will be calculated both on the cumulative year-by-year data and for each year (Years 1 through 10) non-cumulatively.

5.7 Interim Analysis and Data Monitoring

5.6.1 Interim Analyses

Interim analyses will not be conducted for this study. Sequential supplements to the NDA are planned on a rolling basis beginning after the initial filing and are not considered interim analyses.

5.6.2 Data Monitoring Committee

An Independent Data Monitoring Committee (IDMC) will monitor subject safety throughout study conduct, and will be sent reports of all unexpected related serious adverse events (SAEs) that may occur during the study. The IDMC will review all safety data and pregnancy rates, and make recommendations regarding study conduct. Meetings will occur approximately every six months.

5.8 Multicenter Studies

Given that the principal efficacy measure, the Pearl Index, is computed across the combined data across all participating sites, no by-site evaluation or statistical adjustment for site-to-site variation is planned. Summary presentations by site may be considered for specific descriptive variables, e.g., demographic factors, on a by-site basis if warranted.

